Motivation problems (apathy) are common in both Parkinson's disease and psychotic disorders, such as schizophrenia (here typically referred to as negative symptoms). Both disorders are underpinned by abnormalities in dopamine signalling and medications targeting dopamine are routinely prescribed in both disorders. Although representing divergent disorders - Parkinson's disease tends to affect older individuals and predominantly causes movement problems, whereas psychosis typically presents in young adulthood and causes issues with thought and perception - impairments of motivation are common in both conditions. Much recent research has shed light on the cognitive processes and neural pathways underpinning motivated behaviour in health and disease. In both Parkinson's disease and schizophrenia, affected individuals choose to invest less effort in pursuit of goals, which appears to be correlated with negative symptom burden and/or apathy. This research aims to better understand the cognitive processes underlying apathy in individual patients, in particular how self-reported symptoms map onto performance in a decision-making task. The study in particular examines the respective influence of physical effort and monetary reward on decision-making, as well as the impact of having multiple alternatives to choose from in these decisions. A related aim is to observe specific effects of dopamine on decision-making by assessing people with Parkinson's disease in both the medicated and unmedicated state.

Procedure:

The research will aim to recruit 100 people with Parkinson's disease and 100 people with early psychosis, who will perform a novel, computer-based decision-making task incorporating choices that vary in difficulty and the number of alternatives from which to choose, and which either relate to monetary reward or physical effort. Those with Parkinson's disease will be tested in two separate sessions – once in the medicated state (having taken their usual dopaminergic medication), and once after omission of their usual dopaminergic medication. Participants will also complete a number of questionnaires probing symptoms of apathy, depression, fatigue and anhedonia. Primary data will relate to choices (accuracy, reaction time, subjective cognitive effort). Computational modelling (using well-validated evidence-accumulation models) will be fitted to behavioural data, allowing latent processes in decision-making to be examined, and correlated with questionnaire data quantifying motivation in detail. Thus certain apathy scores (or subscores relating to particular 'dimensions' of apathy) may be seen to correlate with computationally-derived parameters reflecting different aspects of decision-making. The study will also incorporate qualitative methodology in a subset of ~10 participants from both clinical groups to explore participants' subjective accounts of motivation problems in order to provide further, detailed information about individual symptoms and experiences.

Funding and support in kind

Funder(s)	Financial and non-financial support given
Wellcome Trust	Funding £15000
University of Birmingham	Sponsor

Role of sponsor and funder

The sponsor and funder have no role in project design, conduct, data analysis and interpretation, manuscript writing, or dissemination of results. Neither the sponsor nor funder controls the final decision regarding any of these aspects of the project.

Roles & responsibilities of management committees/groups & individuals

Patient & public involvement group

Project flow chart Participant identification: Participant identification: -Advertisement (charities such as Parkinson's UK) – individuals -Participant Identification Centres (PICs) - individuals with or at high risk of psychosis, or with Parkinson's with Parkinson's disease -University-held registries of participants with psychosis or with disease) Parkinson's disease Participant screening: Potential participants further screened to determine their eligibility for the study Eligibility assessment: Eligibility assessment: Idiopathic Parkinson's disease, meets inclusion Early psychosis, meets inclusion and exclusion and exclusion criteria (n ~ 100) criteria (n ~100) In-person experiment (~2h): In-person experiment (~2h 5): (participants with early psychosis) (participants with Parkinson's disease -Consent (~5 minutes) session 1) -Decision-making task (~1h 15) -Consent (~5 minutes) -Questionnaires (~35 minutes) -Decision-making task (~1h 15) Medicated or -Debrief (~5 minutes) -Questionnaires (~40 minutes) unmedicated -Debrief (~5 minutes) (counterbalanced sessions on separate days) In-person experiment (~1h 30): participants with Parkinson's disease session 2) -Consent (~5 minutes) -UPDRS III* (~5 minutes) -Decision-making task (~1h 15) -Debrief (~5 minutes) Participant identification for qualitative study ~10 participants identified on basis of quantitative data Qualitative interview (~1h 10) -Consent (~5 minutes) -Interview (~1 hour) -Debrief (~5 minutes)

*UPDRS III refers to part III of Unified Parkinson's Disease Rating Scale (motor exam)

Protocol

Dynamics of motivated decision-making in striatal disorders

Background

Motivational impairments/apathy - often synonymous with a reduced willingness to invest effort in pursuit of goals - are seen in a variety of clinical disorders. They are common in Parkinson's disease and constitute part of the spectrum of 'negative symptoms' in schizophrenia/psychosis, a hallmark of these conditions¹. Although Parkinson's disease and psychosis vary significantly in terms of the neuropathology, epidemiology and clinical features, striatal dysfunction and disturbances of dopamine signalling underpin both disorders and forms the basis of pharmacological treatment. For many years, researchers have postulated that apathy is not one allencompassing entity, but can be dissociated into different component dimensions, possibly relating to different neurological structures or substrates, although conclusive evidence for this is lacking^{2,3}.

A popular method of examining motivation involves an experimental paradigm known as effort-based decision-making, in which participants are asked to choose whether or not to invest physical effort in order to obtain an incentive or reward. Aversion to effort is a frequent and normal observation, both in animal and human experiments, in which the objective value of a reward is discounted by the effort costs and subjects opt to forgo physical effort at the expense of reward^{4,5}. This discounting can be defined mathematically by employing computational modelling to behavioural data and is seen to exhibit a concave or parabolic shape⁶. Previous studies of effort-based decision-making in both Parkinson's disease and schizophrenia have observed that individuals with these disorders experience greater amounts of effort discounting, which appears to be correlated with negative symptom burden and/or apathy^{7,8}. However it remains less well-known how individual's subjective experience of motivation symptoms relates to specific underpinning cognitive processes, such as integration of information about incentives (rewards) and costs such as effort, allocating attention or cognitive resources, or comparing value between different options. The current study would therefore aim to better understand these processes by examining decision-making in two clinical groups in which motivation problems are commonly reported and which are underpinned by dysregulation of dopamine-signalling - people with Parkinson's disease and people with early phase psychosis. The study would specifically investigate how the presence of multiple alternatives can affect decision-making by means of a novel behavioural task where participants either aim to minimise physical effort or maximise a reward – thereby allowing direct comparison between these different choice outcomes. Unlike previous experiments that have largely examined the willingness of participants to put in effort for an incentive, this experiment would more be concerned with the *dynamics* of these choices, employing well-established computational methods to better understand latent processes in these choices. In this way it will be possible to determine things like how physical effort influence decisions, potentially correlating with higher response caution observed in those with apathy, or alternatively apathetic individuals may display lower willingness to invest attention or cognitive resources regardless of the outcome.

2. Rationale

Most existing studies of human motivation have employed binary choices – whether or not participants choose to exert a defined level of effort to receive a reward - which does not necessarily reflect real-world decision-making, where decision-making involves an evaluation of more than two options. It has been observed that the presence of distracting alternatives in multi-option decision-making tasks can affect the valuation of available options^{9,10}, whilst in apathy, sufferers are noted to take longer choosing between options when different alternatives exist¹¹. To date, no studies have explored the effect of multiple alternatives on decision-making in people with apathy. The decisions naturally involve greater complexity and more elaborate computations, and therefore, examination of the observable effects associated with these choices (such as accuracy and reaction times) might be able to shed greater light on specific processes impaired in decision-making in individuals with apathy, both in decisions in which one's choices aim to maximise rewarding outcomes, and in effort-based decisions in which choices determine the subsequent

expenditure of physical effort. We hypothesise that people's apathy ratings from validated questionnaires or individual descriptions of apathy symptoms will map onto performance on these tasks, and may be predictive of things such as aversion to physical effort or allocation of cognitive resources/attention, which can be quantified by applying computational modelling to behavioural data using well-validated evidence-accumulation models.

3. Theoretical framework

This study aims to better understand motivation problems in those with Parkinson's disease and early psychosis (clinical high risk/first episode). We know that motivation impairments are common in these conditions, but for most individuals negative symptoms tend to be simplistically grouped into categories of 'diminished expression' and 'motivation and pleasure'. However, in reality the neuroscience of motivation is complex, with much recent research demonstrating that specific areas of the brain are important in different aspects of decision-making, such as preferentially encoding rewards vs costs¹²,translating incentives onto a common scale of value¹³, controlling and allocating cognitive resources/attention¹⁴, and converting decisions to an appropriate action¹⁵. Despite increased understanding of these processes, we remain unable to correlate someone's individual apathy symptoms with dysfunction at the level of the underlying cognitive processes such as described above.

This study builds on previous experiments using effort- and reward-based decision-making, as well as clinical reports of patients experiencing difficulty in decisions encompassing multiple alternatives. It will examine devaluation of rewards by effort (a hallmark of apathy), whilst also studying effects of multiple alternatives on decision-making. It will also aim to examine specifics effects of dopamine on decision-making, by testing Parkinson's disease patients on and off their usual dopaminergic medication in counterbalanced sessions. Modern computational techniques will be applied to the data to better understand how different parameters affect decision-making in the participants. The research will also aim to examine the subjective experience of apathy in much greater detail than most existing studies, in order to better inform the quantitative analysis.

A proof-of-concept study has already been conducted in healthy adults (under ERN 18-1800E and ERN 20-1897PA). This confirms that the experiment captures expected behaviour (slower and less accurate responding in conjunction with closer-value choices and choices involving more options), with all (n > 60) participants managing to complete the experiment without problems.

4. Research question/aims

Research question: In two clinical disorders underpinned by dopamine dysregulation in which motivation problems are common (Parkinson's disease and those with or at high risk of developing psychosis), does an individual's apathy symptoms predict performance and decision metrics in choices that involve a number of composite processes, including integration of benefits (rewards) and costs (effort), attention and cognitive control, and value comparison in the context of multiple alternative options.

4.1. Objectives

The main objective is to investigate whether different dimensions/subtypes of motivation impairments (apathy) experienced in these conditions - for example cognitive, behavioural, or emotional dimensions of apathy¹⁶ - correlate with performance in tasks which probe different underlying cognitive processes. These include balancing benefits (rewards) and costs (effort), accurately assessing the value of options in decisions encompassing multiple alternatives, and appropriately allocating cognitive resources/control in decisions that vary in terms of choice difficulty. These experiments would extend our current understanding of motivation impairments in these groups of patients and allow us to better characterise the underlying processes affected within individual participants. A secondary objective is to examine the role of dopamine in these same processes, by testing individuals with Parkinson's disease on and off their usual dopaminergic medication in counterbalanced sessions.

4.2. Outcome

Evidence-accumulation (computational) models will be fitted to behavioural data to further understand the dynamics of decision-making. It may be that certain apathy dimensions may correlate with specific computationally-derived parameters – for instance, the behavioural activation dimension may correlate with higher thresholds in effort-based task (greater caution), while the cognitive dimension may correspond to slower drift rates or lower response thresholds. These parameters may show dissociation in effort-avoiding and reward-maximising subtasks.

5. Design and methods of data collection and data analysis

Summary

The design will be a mixed quantitative/qualitative analysis. Quantitative data will be in the form of a computer-based decision-making task and questionnaire measures, primarily of apathy and negative symptoms. Qualitative data will take the form of semi-structured interview in a subset of participants.

Design

Those with or at high risk of psychosis will perform one in-person session, while those with Parkinson's disease will complete two counterbalanced sessions - once having taken their usual dopamine-modulating medication, and once having omitted this medication the same morning. These sessions will take place on separate days within 2 weeks of one another. If participants with Parkinson's disease feel unable to omit their medication, or do not take medication for Parkinson's disease, only a single session will be arranged. Testing will take place in person at the University of Birmingham.

At the point of recruitment, participants will receive a unique identifier. Pseudonymisation will be performed by [name] (JT). The database linking personal data to ID numbers will be maintained by JT in a single, password-encrypted Excel file on the University server. All datafiles generated will only refer to participants with their unique ID numbers.

[figure not shown]
Participants will receive a payment of £25 for participation in a session, plus up to £10 additional payment based on their performance in the task (i.e. up to £35 for a single session).

Behavioural study and questionnaires

(estimated time 1h 30 to 2h 5, depending on clinical group/session number)

- All participants will first receive a brief explanation of the study and provide written consent (~5 minutes).
- Next all participants will complete the computerised decision-making task (~1h 15). In the task, participants will make choices using a computer keyboard, in which the outcome is either physical effort, delivered via a handheld dynamometer (SS25LA, BIOPAC Systems), or a gain or loss of reward credits (that corresponds to an additional bonus payment at the end of the experiment), requiring no physical effort. Reward and effort subsections will be counterbalanced. Data from computer-based tasks (outcomes include reaction times, choice, subjective rating of decision difficulty, force metrics) will be saved as a datafile at the end of the experiment.
- Next participants will complete a set of questionnaires (35 minutes for participants with early psychosis, 40 minutes for people with Parkinson's disease attending their first session; if people with Parkinson's disease are attending for their second session, they will only be required to complete part III of the UPDRS score (a motor exam of ~ 5 minutes duration) and digit span test. Questionnaire data will be collected using the University-approved online survey software Qualtrics or using pen and paper (any paper records will not contain personal information and will be stored in locked filing cabinets within the Centre for Human Brain Health).

The questionnaire battery to be completed by all participants includes:

- -Apathy Motivation Index (~3 minutes)
- -Dimensional apathy scale (~3 minutes)
- -Snaith-Hamilton Pleasure Index (~ 2 minutes)
- -Adapted Glasgow Content of Thought Inventory (~2 minutes)
- -Patient Health-Questionnaire-8 (~2 minutes)
- -Fatigue Severity Scale (~2 minutes)
- -Montreal cognitive assessment (~5 minutes)
- -Forward and backward digit span test (~2 minutes)

All above questionnaires are validated, with the exception of the Glasgow Content of Thoughts Inventory, which is an abbreviated version of an existing, validated questionnaire for insomnia, which has been repurposed to quantify spontaneous cognitive activity/thought.

In addition to the above questionnaires, people with Parkinson's disease attending their first session will complete the validated semi-structured interview questionnaire:

-Unified Parkinson's disease rating scale (~20 minutes)

In addition to the above questionnaires, people with early psychosis will complete the validated semistructured interview questionnaire:

-Brief Negative Symptom Scale (BNSS) (~15 minutes)

People with Parkinson's disease attending their second session will not be required to complete the above questionnaires a second time, but will complete part III of the Unified Parkinson's disease rating scale (motor score, duration ~5 minutes) and forward and backwards digit span tests (~2 minutes).

• Participants will receive a brief debrief about the experiment in their final session and will be invited to be included in a Patient Public Involvement Steering group of research participants (~5 minutes).

Qualitative interview (~10 participants)

(estimated time 1h 10)

A subset of ~10 participants (a similar number with Parkinson's disease and psychosis) will later be invited to participate in a semi-structured interview. These participants will be chosen on the basis of their performance in the initial experiment or questionnaire scores. They will be offered a choice to conduct an interview online (Microsoft teams University of Birmingham account) or in person (School of Psychology, University of Birmingham). The interview will be structured according to the Lille Apathy Rating scale (LARS), a validated semi-structured interview for quantifying apathy according to the dimensions of behavioural activation, emotional responsivity, intellectual curiosity and self awareness. Participant responses will be followed up with follow-up questions that seek to better understand participants' lived experience of motivation problems, focusing on what participants feel and experience rather than simply which activities are impacted. Participants will be given the option to conduct interviews alongside carers or family members. Interview will be conducted by [name], a specialist trainee (ST6) in neurology completing a PhD in neuroscience. Audio from these interviews will be recorded using a passcode-encrypted voice recorder. Audio recordings will not contain any personal information. JT will make a verbal note of participant's identifier code at the beginning of each recording. Interview data will be transcribed into text format by JT as soon as feasibly possible after the interview and within one week. On completion of transcription, audio recordings will be destroyed. Pseudonymised, transcribed interview data will be stored in a single, password-encrypted text file on the university server. The central identifying document linking personal data with participant ID codes will be destroyed at the end of the study period.

Data analysis:

Quantitative data will be analysed using descriptive statistics (such as mean, median), and linear mixed effect models using reaction time and accuracy as dependent variables and questionnaire scores as predictive regressors, using statistical software such as R and Python. Evidence accumulation (drift diffusion) models will be fitted to participant data (using tools such as HDM or DMC including for Bayesian model comparison), and computationally derived parameters (e.g. for drift rate, threshold) will be analysed in linear mixed effect models with questionnaire scores as regressors. Qualitative data from interview will be analysed with interpretative phenomenological analysis by JT, with support and advice by MB.

6. Project setting

All participants attending in person will conduct the experiment in testing rooms at the School of Psychology, [name] where MAJA has dedicated laboratories containing necessary equipment for the experiment. All testing rooms are accessible by lift. Any necessary provisions, including drinks, snacks and walking aids will be provided to participants.

7. Participant recruitment

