13.2. Appendix 2 – schedule of procedures

	Behavioural study (session 1)	Behavioural study (session 2- PwPD only)	Qualitative study
Informed consent	X	X	X
Behavioural study	X	X	
Apathy Motivation Index (AMI)	X		
Dimensional Apathy Scale (DAS)	X		
Fatigue Severity Scale (FSS)	X		
Adapted Glasgow Content of Thoughts Inventory (GTCI)	X		
Patient Health Quesionnaire-8 (PHQ-8)	X		
Snaith Hamilton Pleasure Scale (SHAPS)	Х		
Montreal Cognitive Assessment (MOCA)	Х		
Forward and backward digit span test (~2 minutes)	X		
Unified Parkinson's Disease Rating Scale	Χ	X	
(UPDRS)	(PwPD only)	(part III only)	
Brief Negative Symptom Scale (BNSS)	X		
	(PwPsych only)		
Lille Apathy Rating Scale (LARS)			X
Debrief	X		X

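### Parkinson's participants give their only apathy score at session 1, on medication for some and off for others, so the score carries any effect of an omitted dose and that effect cannot be separated from order group

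*Protocol*

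**What the plan says.** Section 5 (Design) states that "those with Parkinson's disease will complete two counterbalanced sessions", one after usual medication and one after omitting it that morning. The project flow chart agrees: "counterbalanced sessions on separate days". Session 1 is thus medicated for some participants and unmedicated for others.

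Section 5 (Behavioural study and questionnaires) places the battery after the decision task at the first visit: AMI, DAS, SHAPS, PHQ-8, FSS, the adapted thought inventory, MoCA and digit span. For the second visit it says that "People with Parkinson's disease attending their second session will not be required to complete the above questionnaires a second time"; only UPDRS part III and digit span are done then. In Appendix 2 the column "Behavioural study (session 2- PwPD only" is blank for AMI, DAS and the other self-report scales and for the MoCA.

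Section 5 (Data analysis) plans "linear mixed effect models using reaction time and accuracy as dependent variables and questionnaire scores as predictive regressors", and uses the same scores as regressors for the drift-diffusion parameters. Section 4.1 makes apathy against task performance the main objective and the role of dopamine secondary.

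**The concern.** A questionnaire score used as a person-level predictor should be measured under the same conditions in everyone. Here, off-first participants rate apathy, mood and fatigue and take the MoCA after omitting a dose, while on-first participants do so medicated. Whatever the omission does to the answers enters the predictor.

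The protocol links dopamine signalling to motivation and sets out to study dopamine's role in these processes, so it cannot simply assume that the scores are indifferent to drug state. No second apathy score exists for the Parkinson's group as a whole: the LARS goes only to about 10 interviewees across both groups, and the BNSS only to psychosis participants. At stake are the precision of the main analysis and the validity of some narrower ones.

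**Working it through.** The protocol gives no figure on this point, so there is none to reproduce. The shifts below are assumptions shown over a range.

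**Inputs.** From the protocol: battery at session 1 only; counterbalanced order; about 100 Parkinson's participants (section 7.2.1). Assumed: a 50:50 split of order; an off-minus-on shift of dx SD in the score and dy SD in the task outcome; a session 2 practice effect of p SD; a within-person outcome correlation of 0.6; no true association; two-sided 5% tests with Fisher's z at n = 100.

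**1. Aliasing.** For two-session participants, drug state at questionnaire equals order group. A design with an intercept, order group and questionnaire state has rank 2, not 3, so the two effects cannot be separated. Visit number is not mixed with the score, which is always taken at visit 1.

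**2. Outcome averaged over both sessions.** Each person contributes one on and one off session, so order adds no drug shift to the average. In simulations with dx = dy = 0.5 and 0.8, the induced correlation was about 0 and the rejection rate about 5%. A true correlation shrinks by 1/√(1 + dx²/4):

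| dx | factor | power for an assumed r = 0.30 |
|---|---|---|
| 0 | 1 | 86% |
| 0.2 | 0.995 | 86% |
| 0.5 | 0.970 | 84% |
| 0.8 | 0.928 | about 80% |

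**3. Session 1 only, unadjusted.** Induced r = (dx·dy/4) / √[(1 + dx²/4)(1 + dy²/4)]:

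| dx = dy | induced r | false positives |
|---|---|---|
| 0.2 | 0.01/1.01 = 0.01 | about 5% |
| 0.5 | 0.0625/1.0625 = 0.06 | about 9% |
| 0.8 | 0.16/1.16 = 0.14 | about 28% |

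Adjusting for order group returned the simulated correlation to about 0 and the rejection rate to about 5%.

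**4. Apathy by medication.** Let D be the off-minus-on outcome difference. Practice moves D by −p in one order group and +p in the other, a gap of 2p, while the score differs between the groups by dx. So cov = 0.25·dx·2p, and var(D) = 2(1 − 0.6) + p² = 0.8 + p². With no visit term:

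| dx, p | induced r | false positives |
|---|---|---|
| 0.2, 0.3 | 0.03/√(1.01 × 0.89) = 0.03 | about 6% |
| 0.5, 0.3 | 0.075/√(1.0625 × 0.89) = 0.08 | about 12% (12% to 13% in simulation) |
| 0.8, 0.5 | 0.20/√(1.16 × 1.05) = 0.18 | about 44% |

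With p = 0 there is no induced correlation.

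**5. Which covariate repairs step 4.** A fixed effect for questionnaire drug state is constant within a person, so it cancels from D and leaves the bias in place. Visit number changes within a person, so it enters D as order group and absorbs the 2p gap. Simulated at dx = 0.8, p = 0.5, false positives were 48% with the questionnaire-state effect alone (250 replicates) and about 5% with a visit term.

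**The case against.** The strongest reply is that the main analysis is barely touched. The protocol plans mixed models in which two-session participants contribute both drug states, and no analysis restricted to session 1 is announced. Under balanced order the person-level association is only attenuated, and at a 0.5 SD shift the loss of power is about two percentage points. This stands.

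Second, nothing in the documents shows that these scales move with one delayed dose. Section 10.1 and the risk assessment list only motor effects, and no recall periods are given. This also stands: the size is unknown and may be nil.

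Third, visit and order terms are ordinary contents of an analysis plan that is not shown here. That is fair as to the model. It does not settle the schedule: when the score is taken is fixed by the protocol, and no later model can supply a score in the other state.

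A reader might infer that the design creates a spurious apathy–performance correlation in the main objective, or that around 44% false positives should be expected. The documents support neither. The first needs an unadjusted session 1 analysis. The second needs the top of the assumed range and an omitted visit term, and the protocol does not say that visit will be left out. A reader might also count the 75 minutes of task before the questionnaires as part of this problem, but that applies to all participants in either drug state.

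**Conclusion.** The point holds as a modest, avoidable weakness in how the main predictor is measured in the Parkinson's group. The schedule is unambiguous (high confidence); the consequence is uncertain (medium confidence), because the shift in scores is not documented.

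For session-averaged outcomes with balanced order, expect attenuation by a factor between 0.995 and 0.928 over assumed shifts of 0.2 to 0.8 SD. Bias is confined to unadjusted session 1 analyses (about 5% to 28% false positives over that range) and to apathy-by-medication models without a visit term (about 6% to 12% for score shifts of 0.2 to 0.5 SD with 0.3 SD practice, and about 44% only at 0.8 and 0.5 SD).

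These figures rest on balanced order. Section 7.2.2 sees no rationale for randomisation, while the risk assessment (section 13.4, part 2.2) says that medication order is randomised; the two should be reconciled. They also leave out single-session Parkinson's participants (those unable to omit medication or not taking any), whose drug state does not follow the counterbalancing.

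**What to change.** **Schedule.** For two-session Parkinson's participants, collect the self-report battery in one drug state for everyone. Either give it at the medicated session, whichever visit that is, or send the self-report forms through Qualtrics (already in use) on a usual-medication day before visit 1. Give the MoCA at the medicated session. Amend section 5, the flow chart and Appendix 2. No medication instruction changes.

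**Cost.** If the forms are given at the medicated visit, off-first participants move 3+3+2+2+2+2 = 14 minutes of self-report and 5 minutes of MoCA from visit 1 to visit 2. Visit 1 falls from 125 to 106 minutes. Visit 2 rises from 92 (90 in the flow chart plus 2 for digit span) to 111. Questionnaire visit number would then vary with order group; sending the forms beforehand avoids this for the self-report scales. Those who do not return after an unmedicated first visit would need the online forms.

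**Data already collected.** Adjust for order group (the same variable as drug state at questionnaire) in person-level and session 1 analyses. In any apathy-by-medication model include visit number, or equivalently medication by order. A fixed effect for questionnaire drug state alone is not enough there.
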